**2.2. Secondary objectives**

- To assess the VE in the prevention of HZ over the total duration of the ZOSTER-049 study as measured by the reduction in HZ risk in subjects within each of the age ranges\* at the time of first vaccination in the ZOSTER-006/022 studies;
- To assess the VE in the prevention of HZ from one month post dose 2 in the ZOSTER-006/022 studies until the end of the ZOSTER-049 study as measured by the reduction in HZ risk in subjects  $\geq 50$  YOA overall and within each of the specified age ranges\* at the time of first vaccination in the ZOSTER-006/022 studies;
- To assess the VE in the prevention of HZ over each year of follow-up from one month post dose 2 in the ZOSTER-006/022 studies as measured by the reduction in HZ risk in subjects  $\geq 50$  YOA overall and within each of the specified age ranges\* at the time of first vaccination in the ZOSTER-006/022 studies;

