**CONFIDENTIAL**

201190 (ZOSTER-049 EXT:006-022)  
Protocol Amendment 5 Final

The primary analysis will be to assess the VE during this study and will use the historical control estimates adjusted for age at randomisation during the ZOSTER-006/022 studies. The method using the historical control estimates will be further explained in the Statistical Analysis Plan (SAP). Vaccine effects will be estimated by calculating the VE and estimating 95% CIs based on the variance of the observed population in this study and treating the historical control as constant.

The secondary analysis will be to assess the VE over each year of follow-up. Results from the ZOSTER-006/022 studies will be pooled for each year after vaccination with methods used in these studies. For overlapping years between ZOSTER-006/022 studies and this study, all the data will be pooled. For the non-overlapping years only the data from this ZOSTER-049 study will be used.

The assessment of the VE over the overall period including period from vaccination during the ZOSTER-006/022 studies up to the end of this long-term study will be done with a method that will be described in the SAP.

Any available information for the diagnosis of HZ episodes (clinical diagnosis, PCR, laboratory methods, etc.) during the interval between the end of the ZOSTER-006/022 studies and beginning of the ZOSTER-049 study is to be collected. Confirmation of all of these cases in the exact way as what will be done for cases collected during the clinical study follow-up periods of the ZOSTER-006, ZOSTER-022 and ZOSTER-049 will not be possible. Therefore, these cases will not be part of all efficacy analyses. A sensitivity analysis to assess the impact of these cases on the VE will be performed (this will be described in the SAP).

The purpose of these analyses will be descriptive and therefore the CIs will not be adjusted for multiple testing.

The analyses will be performed for confirmed HZ cases, for PHN and for complications (other than PHN).

Any exploratory or sensitivity analysis may be performed in addition to the analyses described above on an ad-hoc basis. However, the significance level of those analyses may not be fully controlled.

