**Table 1 Efficacy analyses per study periods and age-strata**

Analysis	Study period	≥ 50 YOA	≥ 60 YOA	≥ 70 YOA	50-59 YOA	60-69 YOA	70-79 YOA	≥ 80 YOA	Objective
A	Z-049 duration overall	X	X	X	X	X	X	X	Primary and Secondary
B	Z-006/Z022 * + Z049 duration overall	X	X	X	X	X	X	X	Secondary
C	Z-006/022 + Z-049 duration yearly**	X	X	X	X	X	X	X	Secondary and CCI

YOA = Year of age

\* from one month post dose 2 in the ZOSTER-006/022 studies

\*\* yearly follow-up will be computed from one month post dose 2 in the ZOSTER-006/022 studies. Note that results from the pooled ZOSTER-006/022 studies will be presented for each year after vaccination with methods used in these studies.

The primary analysis of efficacy will be performed on the mTVC, the analysis will be also performed on the TVC for efficacy and the ATP for efficacy to complement the mTVC analysis.

The **VE analysis for HZ** on TVC, mTVC and ATP cohort for efficacy over the study duration of present study ZOSTER-049 will be performed over the follow-up time calculated from enrolment in the present study to the time of first confirmed HZ case for a subject with a confirmed HZ case, and to the date of last contact for subjects without the occurrence of confirmed HZ case.

The **VE analysis for HZ** on mTVC and ATP cohort for efficacy over the duration starting from ZOSTER-006/ -022 study will be performed over the follow-up time calculated from one month post Dose 2 to the time of first confirmed HZ case for a subject with a confirmed HZ case, and to the date of last contact for subjects without the occurrence of confirmed HZ case.

The **VE analysis for HZ** on the TVC will be performed over the complete follow-up period and will include confirmed HZ cases from Dose 1 administered in the ZOSTER-006/022 studies for vaccine efficacy evaluation. The end of the follow-up period will be calculated according to the same principle as will be done for the mTVC and ATP analyses for efficacy, i.e., up to the confirmed HZ case for a subject with a confirmed HZ case, or up to the date of last contact for subjects without a confirmed HZ case.

***In the VE analysis for PHN and HZ related complication (other than PHN), the follow-up time will be calculated in the similar way as in VE analysis for HZ.***

All above analyses will be performed overall and by age strata. The age strata for VE are defined as: **50-59, 60-69, 70-79, ≥80, ≥60, ≥70 YOA** at primary vaccination in ZOSTER-006/022 studies.

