#### 6.2.2.3. **Sensitivity analysis considering subjects aging when enrolled into ZOSTER-049 from ZOSTER-006/022**

*Since all subjects enrolled in ZOSTER-049 study had aged for ~5 years compared to when they were enrolled in ZOSTER-006/022 studies, a sensitivity analysis on VE (analysis A, B and C on mTVC - LTFU and Control group only.) is planned to consider the aging factor on ZOSTER-049 subjects when utilizing the historical control to estimate the incident rate on the hypothetical control in ZOSTER-049 study. Please refer to Section 7.3.6 for more details*

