### 7.3.3. Method for determining Historical Control Reference Group for Planned Analysis

The proposed model is specified prior to performing any interim analysis and is based on analysis performed on previous studies ZOSTER-006/022.

*Since there is no concurrent placebo group in ZOSTER-049, incidence rates estimations on the hypothetical Control group in ZOSTER-049 study are done by utilizing Poisson regression model using data from the Placebo group in ZOSTER-006/022 study to obtain the coefficients for region and by age strata (based on age on primary vaccination). The resulting estimated incidence rate adjusted for region and by age strata are then multiplied by the actual follow-up (FU) time observed in the ZOSTER-049 study (all vaccinated subjects) to obtain the estimated number of HZ cases on the hypothetical Control group. The same incidence rate estimates by region and by age strata will be used in both yearly and overall VE calculation.*

The statistical methodology used to estimate the incidence rate on the hypothetical ZOSTER-049 control from the historical control reference group is described below. The calculation of the vaccine efficacy is based on the methodologies used in the Merck paper (Morrison) and will be done stepwise as described below:

1. Poisson regression models are used to estimate the incidence rate for HZ for the ZOSTER-049 study hypothetical placebo group based on historical controls from ZOSTER-006/022 study:

A Poisson regression model based on placebo's HZ rates in ZOSTER-006/022 studies is developed for estimating the regression coefficient in each age strata (age at first vaccination in ZOSTER-006/022 studies): **50-59, 60-69, 70-79, ≥80, ≥ 60, ≥ 70 YOA.**

$$\text{Ln}(r_{\text{HZplacebo in zoster-006/022}}) = \alpha + \beta_{\text{Australasia}} * \text{RegionAustralasia} + \beta_{\text{Europe}} * \text{RegionEurope} + \beta_{\text{North America}} * \text{RegionNorth America} + \beta_{\text{Latin America}} * \text{RegionLatin America}$$

Where

- $\text{Exp}(\alpha)$  = mean HZ rate across all regions
- Region\_Australasia, Region\_Europe, Region\_North America, Region\_Latin America are indicator variable(1/0)
- $\beta_{\text{Australasia}}, \beta_{\text{Europe}}, \beta_{\text{North America}}, \beta_{\text{Latin America}}$ : estimated region-specific Poisson regression coefficients for HZ rate.

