***To note - North America is used as reference group***

2. Determine the Age adjusted historical control rate:

Using the coefficients from the Poisson regression in (1), the age-specific HZ incidence rates for an age stratum for Placebo group will be calculated as:

$$\text{Age specific } r_{\text{HZhistorical control reference group}} = \exp(\alpha + \beta_{\text{Australasia}} * \text{Region_Australasia} + \beta_{\text{Europe}} * \text{Region_Europe} + \beta_{\text{Latin America}} * \text{Region_Latin America})$$

Once the age-specific incidence rates are calculated for the historical control data from the ZOSTER-006 and ZOSTER-022, the results will be used to calculate age-specific controls rates on the hypothetical control group for the ZOSTER-049 interim and final analyses.

3. Determine the number of HZ cases for the age adjusted historical controls:

For each scheduled analysis, the age-specific follow-up time observed in ZOSTER-049 will be used as the follow-up time on the corresponding age-specific hypothetical control on ZOSTER-049. The total number of subject-years of HZ surveillance ( $F_{\text{Age}}$ ) for each age-strata will be then multiplied by the age-specific incidence rate that was estimated from step 2, to obtain the expected number of evaluable cases of HZ ( $n_{\text{Age}}$ ) for a specific age strata in the hypothetical control in ZOSTER-049:

$$n_{\text{Age}} = F_{\text{Age}} * \exp(\alpha + \beta_{\text{Australasia}} * \text{RegionAustralasia} + \beta_{\text{Europe}} * \text{RegionEurope} + \beta_{\text{Latin America}} * \text{RegionLatin America})$$

Once the expected number of cases for the hypothetical controls are determined for each age strata, expected HZ incidence rate for the hypothetical controls will be calculated by summing the numbers of expected evaluable cases of HZ for each age strata, and dividing by the total number of subject-years of HZ surveillance among all subjects during the ZOSTER-049 study.

*For the overall calculation of VE starting from the ZOSTER-006/022 study, the observed incidence rate for Placebo during ZOSTER-006/022 and the predicted incidence rate during ZOSTER-049 will be used in the calculation.*

*In the situation that there are very few subjects during the last year of follow-up with limited total follow-up time, data from both year 11 and year 12 will be pooled in the VE analysis.*

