*For the sensitivity analysis considering subjects aging when enrolled into ZOSTER-049 from ZOSTER-006/022. The same step 1,2 and 3 will be used to calculate the incidence rates on ZOSTER-049 historical control using data from ZOSTER-006/022 control. The only difference is that estimated incidence rates will be applied to the age-specific group based on the approximate age in years when the subjects were enrolled in the beginning of study ZOSTER-049 to estimate the HZ cases in the hypothetical control.*

*For the VE analysis for PHN or HZ related complication (other than PHN) the same poison regression models detailed in step 1, 2 and 3 will be used to generate the hypothetical controls for the incidence of PHN or HZ related complication (other than PHN) in study ZOSTER-049.*

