## CONFIDENTIAL

201190 (ZOSTER-049 EXT:006-022)  
Statistical Analysis Plan Amendment 3

ZOSTER-006/022 control		ZOSTER-049 hypothetical control (estimated HZ cases to be used in 049 VE analysis)				
55-59 YOA (at primary vaccination )	IR2	55-59 YOA (at Z-049 enrollment)	N1	FT_1	IR2	$n1=FT1*IR2$
60-64 YOA (at primary vaccination )	IR3	60-64 YOA (at Z-049 enrollment)	N2	FT_2	IR3	$n2=FT2*IR3$
65-69 YOA (at primary vaccination )	IR4	65-69 YOA (at Z-049 enrollment)	N3	FT_3	IR4	$n3=FT3*IR4$
70-74 YOA (at primary vaccination )	IR5	70-74 YOA (at Z-049 enrollment)	N4	FT_4	IR5	$n4=FT4*IR5$
75-79 YOA (at primary vaccination )	IR6	75-79 YOA (at Z-049 enrollment)	N5	FT_5	IR6	$n5=FT5*IR6$
80-84 YOA (at primary vaccination )	IR7	80-84 YOA (at primary vaccination)	N6	FT_6	IR7	$n6=FT6*IR7$
>=85 YOA (at primary vaccination )	IR8	>=85 YOA (at Z-049 Enrollment)	N7	FT_7	IR8	$n7=FT7*IR8$

The resulting HZ cases for age strata defined by subjects' age at first vaccination in ZOSTER-006/022 studies are then calculated in the following way which are to be used in the VE sensitivity analysis by strata following the same methodology used in VE Analysis A, B and C:

HZ cases for 50-59 YOA:  $n1+n2$

HZ cases for 60-69 YOA:  $n3+n4$

HZ cases for 70-79 YOA:  $n5+n6$

HZ cases for >=80 YOA:  $n7$

Since all subjects in ZOSTER-049 study were  $\geq 55$  YOA at their enrollment, for the overall VE sensitivity analysis, subjects who were 50-54 YOA at primary vaccination were excluded from the ZOSTER-006/022 Placebo group when building the

*hypothetical control. The estimated IR are then multiplied by the total follow-up time observed in ZOSTER-049 study to obtain the estimated HZ cases, which will be subsequently used to calculate overall VE following the same methodology used in VE Analysis A, B and C.*

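### Yearly vaccine efficacy: the ageing sensitivity analysis resets age only once, at ZOSTER-049 enrolment, so constant efficacy can still look like waning in later years

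*SAP*

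**What the plan says.** VE by year is a secondary objective (Protocol 2.2): "To assess the VE in the prevention of HZ over each year of follow-up from one month post dose 2". The SAP calls it Analysis C, and the footnote to SAP Table 1 sets the index: "yearly follow-up will be computed from one month post dose 2 in the ZOSTER-006/022 studies". Protocol 11.7.2 says which data feed the later years: "For the non-overlapping years only the data from this ZOSTER-049 study will be used". Those years have no concurrent placebo group.

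The control for them comes from a Poisson model of ZOSTER-006/022 placebo rates, by age at primary vaccination and region (SAP 7.3.3): "The same incidence rate estimates by region and by age strata will be used in both yearly and overall VE calculation".

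SAP 6.2.2.3 adds a sensitivity analysis to Analyses A, B and C because "all subjects enrolled in ZOSTER-049 study had aged for ~5 years compared to when they were enrolled in ZOSTER-006/022 studies". SAP 7.3.3 says its only difference from the main method is that "estimated incidence rates will be applied to the age-specific group based on the approximate age in years when the subjects were enrolled". The table in SAP 7.3.6 carries this out: each 5-year band of enrolment age has its whole ZOSTER-049 follow-up time multiplied by one placebo rate. Neither document moves person-time to an older band as subjects age during ZOSTER-049.

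**The concern.** Protocol 1.1 says incidence rises progressively with age after 40. Vaccinated subjects grow older through about six years of ZOSTER-049, while their projected control stays at one age. Even if the vaccine's relative protection never changes, cases in the vaccinated cohort rise and expected control cases do not, so estimated VE falls year by year. The main analysis has this drift, and understates VE wherever incidence is still rising. The check shifts the control by about five years, once, and then holds it flat again.

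At stake is the reading of persistence. Protocol 1.2.1 ties possible waning to a possible need for additional doses. A reader who sees a decline survive the ageing check could conclude that ageing has been ruled out as its cause. The confidence intervals would not warn of this, because SAP 6.2.1 treats the historical control as constant.

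**Working it through.** The plan gives no figure for this effect, so there is none to reproduce. The size below comes from an expected-case calculation.

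**Inputs from the documents**
- Incidence: 5 per 1000 a year at 50-59 and 10 per 1000 from 60 (Protocol 1.1).
- Placebo follow-up: about 4 years (Protocol 1.2.1).

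**Assumptions**
- True VE is 80% in every year.
- Entry age is uniform within each 10-year stratum.
- ZOSTER-049 enrolment is spread evenly over 4-6 years after dose 2.
- The few months between first vaccination and the start of the yearly count are ignored.
- Four incidence curves: a step from 5 to 10 at age 60; linear ramps over ages 55-65 and 52.5-67.5; 2% growth a year.

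**Formula.** Estimated VE in year y = 1 − 0.20 × R(y)/C. R(y) is the true unvaccinated rate at the ages reached in year y, and C is the control rate the plan would use.

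**50-59 stratum, step curve, by hand**
- R: the midpoint of Year 7 is 6.5 years after dose 2, so 65% of the stratum is 60 or older: 0.35×5 + 0.65×10 = 8.25. In Year 10 (midpoint 9.5): 0.05×5 + 0.95×10 = 9.75.
- Main analysis: placebo time averages 2 years after entry, so 2/10 = 20% of it lies at 60 or above. C = 0.8×5 + 0.2×10 = 6.0. VE = 1 − 0.2×8.25/6.0 = 72.5% in Year 7 and 1 − 0.2×9.75/6.0 = 67.5% in Year 10.
- Ageing check: placebo rates by entry band are 5.0 (50-54), 0.6×5 + 0.4×10 = 7.0 (55-59) and 10 (60 and over). At enrolment 2.5% are under 55, 47.5% are 55-59 and 50% are 60 or older, so C = 0.025×5 + 0.475×7 + 0.5×10 = 8.45. VE = 1 − 0.2×8.25/8.45 = 80.5% in Year 7 and 1 − 0.2×9.75/8.45 = 76.9% in Year 10.
- SAP 7.3.6 says nobody was under 55 at enrolment. With everyone enrolled at exactly 5 years, C = 0.5×7 + 0.5×10 = 8.5, and VE runs from 80.6% to 77.1%, a fall of 3.5 points. The 2.5% does not drive the result.

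**2% growth.** Only the age gap between vaccinee and control time matters.
- Main: gaps of 6.5−2 = 4.5 and 9.5−2 = 7.5 years give 1 − 0.2×exp(0.09) = 78.1% and 1 − 0.2×exp(0.15) = 76.8%.
- Check: the control sits at about 5+2 = 7 years, so the gaps are −0.5 and 2.5 years: 1 − 0.2×exp(−0.01) = 80.2% and 1 − 0.2×exp(0.05) = 79.0%.

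**All four curves, 50-59, Year 7 to Year 10** (ramps by numerical integration of the same formula)

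| Curve | Main analysis | Ageing check | Fall in check |
|---|---|---|---|
| Step at 60 | 72.5 to 67.5 | 80.5 to 76.9 | 3.6 |
| Ramp 55-65 | 73.8 to 70.5 | 80.3 to 77.8 | 2.5 |
| Ramp 52.5-67.5 | 75.5 to 72.6 | 80.4 to 78.1 | 2.3 |
| 2% a year | 78.1 to 76.8 | 80.2 to 79.0 | 1.2 |

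With enrolment spread over 3.5-6.5 years (the range of first-visit timeframes in SAP 6.3.3), the fall is 1.2-3.4 points.

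**Other strata and all ages.** Under the step and ramps the check reads 79.9-80.0% in both years for 60-69 and 70-79; under 2% growth it falls 1.2 points there too. For all ages under the step, a 20% share for 50-59 gives R = 9.65 then 9.95 against C = 9.69, so 80.1% then 79.5%. A 40% share gives 80.2% then 78.9%. Across the four curves the all-ages fall is about 0.4-1.3 points.

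**Whole of ZOSTER-049** (Year 1 to Year 6, enrolment at 5 years; not a planned table). For 50-59 the check falls 2.0-5.3 points against 2.2-7.5 in the main analysis. At true VE 90% the check falls 1.0-2.6 points. A separate calculation with smooth growth of 1-4.6% a year over uniform ages gave 1.0-5.0 points in the check against 1.0-6.0 in the main analysis, at VE 80%.

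**Analysis A in the check:** 78.9-79.6% for 50-59 and 79.5-79.9% for all ages.

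**The case against.** **Sampling error is larger.** About 6000 evaluable subjects (Protocol 11.4.1) at 10 per 1000 give 60 expected cases a year. Twelve observed against a fixed 60 gives an exact Poisson interval of about 65-90%, and 2 against 10 gives 28-98%. No single year could show the drift. This stands, but the drift runs in one direction whenever incidence rises with age, and the trend is what will be read.

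**It is largely one stratum.** On the protocol's two numeric rates, the check drifts only in 50-59. Drift above 60 needs incidence to keep rising there, which Protocol 1.1 suggests but does not quantify. This stands as a limit on size.

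**The bias is conservative.** In late years VE is understated, so a false claim of lasting protection cannot arise from it. True, but a false suggestion of waning can.

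**The check does what it says.** SAP 6.2.2.3 speaks only of ageing up to enrolment, and for Analysis A it works. Applying it to Analysis C, a yearly series, is where it falls short.

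**The analyses are descriptive and already caveated.** Protocol section 2 sets no success criteria, and SAP 7.3.1 says the estimates are not equivalent to those from a controlled trial and asks for caution in comparing them with ZOSTER-006/022. Neither mentions ageing within follow-up.

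**The remedy is partial.** It leaves the main Analysis C unchanged and does not help ≥80. This also stands.

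**Conclusion.** The concern holds and should be acted on, though it does not threaten the primary result. The ageing check resets the control's age once and leaves most of the age-driven slope in the yearly series: under the step curve, 3.6 of the main analysis's 5.0 points (72.5 − 67.5) between Years 7 and 10. On the planned index the false fall is 1.2-3.6 points for 50-59 and about 0.4-1.3 for all ages at true VE 80%. It slightly overstates VE early and understates it late.

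The mechanism follows directly from the text. The size rests on assumed incidence curves, age mix and enrolment timing, because the documents give only two rates; with no age gradient there is no effect. Years with concurrent ZOSTER-006/022 placebo data only are unaffected.

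**What to change.** In SAP 7.3.6, for the Analysis C ageing sensitivity analysis:

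- Split both ZOSTER-006/022 placebo person-time and ZOSTER-049 person-time by attained 5-year age band, updated through follow-up.
- Estimate placebo rates by attained band with region in the model, and apply them to the matching ZOSTER-049 person-time.
- Sum expected cases within each subject's own vaccination-age stratum, and take the overall figure as the sum across strata.
- State that the open top band may need pooling, so the ≥80 yearly trend can keep some ageing drift.

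In the same calculation this brings the 50-59 stratum to 79.7-80.0% in Years 7 and 10.

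Two wording repairs can go in with it; neither adds weight to the concern. The overall paragraph of SAP 7.3.6 ("The estimated IR are then multiplied by the total follow-up time observed in ZOSTER-049 study to obtain the estimated HZ cases") can be read as one pooled rate times total time, whereas SAP 7.3.3 step 3 builds the overall "by summing the numbers of expected evaluable cases of HZ for each age strata"; align the two. The ZOSTER-049 label of the 80-84 row in 7.3.6 refers to primary vaccination, while the other rows refer to enrolment.

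The cost is SAP text and modest programming. SAP 7.2 already derives enrolment age as age at first vaccination plus elapsed time, and the same rule extends to later dates. The downside is sparse placebo data at the oldest ages. With an open ≥85 band the split does not help ≥80: under 2% growth the ZOSTER-049 Year 1 to 6 fall is 2.0 points in the current check and 2.1 with the split. A ≥90 band would cut it to 0.1-0.2 but would rest on about 4-14% of the ≥80 placebo time, on an assumed age mix.

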#### **7.3.4. Method for computing VE and the associated CIs**

Once estimated data for the hypothetical control are generated as per steps listed in Section 7.3.2, following similar approach in ZOSTER-006/022, Poisson regression model will be used to estimate VEs and the associated CIs for all the planned VE analysis. Region will be included as a fixed effect and analysis will be performed on the following age strata ((50-59, 60-69, 70-79, ≥80, ≥60, ≥70 YOA) separately and overall.

*In the situation that there is no case in HZ/su group and >0 cases in Placebo group, VE and UL of VE will be set to be 100%. In the situation that there is >0 cases in HZ/su group and 0 case in Placebo group, VE and CI of VE will be set as “not available” (“-” or “U”).*

